3.2 Exclusion Criteria

1. Pregnant
2. Cognitively impaired
3. Incarcerated
4. Complete hysterectomy
5. History of cervical treatment for abnormal Pap/HPV test (i.e., cryotherapy, Loop electrosurgical excision procedure(LEEP))

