3.3 Early Withdrawal of Subjects

3.3. 1 Criteria for removal from study

If the subjects becomes pregnant or does not complete the study activities they will be removed from the study.

3.3. 2 Follow-up for withdrawn subjects

The withdrawal will be documented and the subject will be replaced if the timeline allows.

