4.0 Recruitment Methods

4.1 Identification of subjects

Potential participants will be identified from participating Family and Community Medicine (FCM) and OBGYN clinics at Penn State Health when they are determined to have abnormal findings on Pap/HPV test that requires a colposcopy for follow-up. Potential participants will be identified in one of three ways:

(1) A member of the study team will access the electronic medical records (EMR) for [name] and [name] OBGYN patients that meet the study criteria and have an upcoming colposcopy appointment. Then, a member of the study team will call the participant about possible involvement in the study.

(2) Clinicians will provide general information (via recruitment cards) about the study during the colposcopy appointment (if the patient was not previously contacted or was scheduled less than two weeks from their appointment). Patients will be advised to contact the study team using the information on the card if interested in participating.

(3) After a patient's appointment, if the clinician believes the individual could meet eligibility criteria for the study, the clinician will send the contact information for these patients to the study team members

through a secure message in the Electronic Medical Record. For this option, patients would not have been presented with the research opportunity during their appointment; clinicians may not have had a recruitment card available to give to their patient or may simply have forgotten to share the study opportunity.

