4.2 Recruitment process

4.2. 1 How potential subjects will be recruited.

Clinicians will identify potential participants they think would be eligible for the study and provide some general information (via the recruitment cards) to the participants. Members of the study team (non-clinical staff) will prospectively review clinic schedules in order to identify potential participants, and clinicians may also identify patients after their scheduled appointment. This will ensure that enrollment numbers are met and that all potentially eligible participants are provided with a recruitment card by their clinician or contacted directly by a study team member.

4.2. 2 Where potential subjects will be recruited.

Potential subject will be recruited from Penn State Health Family & Community Medicine and OBGYN clinics.

4.2. 3 When potential subjects will be recruited.

Participants will be recruited at their colposcopy appointment in the clinician's office or over the phone by a study team member. The participant will be screened for eligibility and provide verbal implied consent.

4.2. 4 Describe the eligibility screening process and indicate whether the screening process will occur before or after obtaining informed consent. Screening begins when the investigator obtains information about or from a prospective participant in order to determine their eligibility. In some studies, these procedures may not take place unless HIPAA Authorization is obtained OR a waiver of HIPAA Authorization when applicable for the screening procedures is approved by the IRB. [For FDA regulated studies, consent for any screening activities would need to be obtained prior to screening unless specifically waived by the IRB.]

Initial screening may occur before obtaining implied consent. A member of the research team will review the EMR for FCM/ OBGYN patients that meet the study criteria. Then a study team member will call the person to complete the screening process and then obtain verbal consent. A study team member will mail the participant the study materials and a summary explanation of research.

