5.2 Obtaining Informed Consent

5.2. 1 Timing and Location of Consent

Participants will be consented up to 21 days before or after their colposcopy appointment over the phone and answers will be input into REDCap by a member of the study team. Once the participant has been screened and gives verbal consent, participants will be mailed a paper copy of the summary explanation of research with the HPV self-sampling kit.

5.2. 2 Coercion or Undue Influence during Consent

After a review of the research study via the Summary Explanation of Research, subjects will be asked if they give consent to participate in the survey. Subjects will be reminded that they may refuse to answer any question and end their participation at any time, and their decision on whether or not to participate in this research will not affect their medical care.

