Participants must complete the self-sampling kit within 14 days before or after their colposcopy visit, meaning that there is a 28 day window for participants to collect the sample. A 2nd HPV self-sampling kit will only be mailed if the participant states that she lost or did not receive the first one. Participants will receive a maximum of 2 HPV self-sampling kits.

Once the HPV self-sampling kit has been returned and the survey completed, the study participants will be mailed an incentive in the form of a Greenphire ClinCard, and a thank you letter from the PI. Analysis of the self-sampling specimens will be conducted to determine HPV DNA positivity to compare to the results of the previous Pap test, HPV test, and colposcopy. EMR data will be used to check insurance status, and the date and result of Pap test, HPV test, and colposcopy.

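### Exclusion 5 is undated and later cervical treatment is not recorded, so a post-treatment self-sample can be paired with a pre-treatment clinician result (minor)

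*Combined protocol and SAP*

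**What the plan says.** Exclusion 5 in section 3.2 bars women with "History of cervical treatment for abnormal Pap/HPV test", with cryotherapy and LEEP as its examples. It names no date or event before which the treatment must have happened.

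Eligibility is completed by phone. For women found through the EMR, section 4.2.4 says: "Then a study team member will call the person to complete the screening process and then obtain verbal consent". Section 5.2.1 sets the timing: "Participants will be consented up to 21 days before or after their colposcopy appointment over the phone". Section 4.1 gives three recruitment routes: an EMR search for women who "have an upcoming colposcopy appointment", a card handed over at the visit, and referral by the clinician after it.

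Once a woman is enrolled, section 3.3.1 gives the only grounds for removal: "If the subjects becomes pregnant or does not complete the study activities they will be removed from the study".

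On timing of the sample, section 7.1 says: "Participants must complete the self-sampling kit within 14 days before or after their colposcopy visit". Women who have not used the kit by the call 3 to 5 days before the visit are told to wait until after it. The self-sample is then compared with the earlier Pap and HPV tests and with colposcopy. The EMR items listed in section 7.1 are insurance status and the dates and results of the Pap test, HPV test and colposcopy.

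**The concern.** The comparison assumes that the self-sample and the clinician sample describe the same cervix in the same state. Treatment between the two breaks that assumption. If treatment clears the infection or removes the infected tissue, a correct negative from the kit is set against a correct positive from the clinician and scored as a failure of the kit.

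The plan has three places where such a pair could be caught, and none does so. The exclusion is undated and checked only at screening. The withdrawal rule carries pregnancy forward from the exclusion list but not treatment. The data abstraction does not ask about treatment, so the pair could not be recognised at analysis.

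The gap may also be hard to close afterwards. Section 6.2.1.2 has the list linking record number to study ID destroyed after data collection, and a treatment date not taken by then may not be recoverable. With 30 completers, a single pair moves the agreement statistics visibly.

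**Working it through.** The plan has no figure of its own on this point. The 30 in section 8.2 does not bear on it. The check is therefore a reading of the sections together, followed by an illustration of size.

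**Step 1: can a post-treatment self-sample enter?** Take a woman treated after her clinician Pap/HPV test who self-samples after both the visit and the treatment, within the 14 days allowed by section 7.1. The answer depends on how *history* is read.

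| Reading of exclusion 5 | Screening call before treatment | Screening call after treatment |
|---|---|---|
| Any treatment before the screening call | passes; later treatment is not a ground for removal | excluded |
| Treatment for an earlier abnormality only | passes | passes |

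Under the first reading the pair can arise only among women enrolled before the treatment. These are mainly women phoned before the visit, but also a woman enrolled after colposcopy and treated later, before she samples. Under the second reading it can arise by every route. Neither reading closes the gap.

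**Step 2: could it be seen at analysis?** The collection date is available, because section 7.4.6.3 has the participant write it on the requisition form. The treatment date is not among the listed EMR items, so the order of the two cannot be established from the planned data.

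**Step 3: size per woman.** The documents give no rate of treatment in the window, no expected agreement and no prevalence. The table below is an assumption: 30 women, of whom 18 are positive on both, 3 clinician-positive only, none self-positive only and 9 negative on both. Each affected woman is assumed to move from both-positive to clinician-positive only.

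Kappa = (po − pe)/(1 − pe), where po is observed agreement and pe is the agreement expected from the margins.

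- None affected: po = 27/30 = 0.900; pe = (21×18 + 9×12)/900 = 486/900 = 0.540; kappa = 0.360/0.460 = 0.783.
- One affected (17, 4, 0, 9): po = 26/30 = 0.867; pe = (21×17 + 9×13)/900 = 474/900 = 0.527; kappa = 0.340/0.473 = 0.718.
- Two affected (16, 5, 0, 9): po = 25/30 = 0.833; pe = (21×16 + 9×14)/900 = 462/900 = 0.513; kappa = 0.320/0.487 = 0.658.
- Three affected (15, 6, 0, 9): po = 24/30 = 0.800; pe = (21×15 + 9×15)/900 = 450/900 = 0.500; kappa = 0.300/0.500 = 0.600.

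Each such woman lowers kappa by about 0.06 and agreement by about 3 points.

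**Step 4: effect of leaving the pair out.** With one affected woman omitted, the table is (17, 3, 0, 9) on 29 pairs: po = 26/29 = 0.897; pe = (20×17 + 9×12)/841 = 448/841 = 0.533; kappa = 0.364/0.467 = 0.779. In this illustration, omission brings kappa back to 0.78.

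**The case against.** The strongest reply is that the triggering event appears nowhere in the documents. No section says that treatment is given at the visit or within the self-sampling window; section 7.1 says only that colposcopy follows usual practice. A pair is affected only if the woman was clinician-positive, had not sampled before the visit, was treated by about day 14, sampled after that treatment, and turned HPV-negative in that time. On the first reading she must also have enrolled before the treatment. No frequency is given for any of these steps. This stands: the count may be zero, and the movement to 0.66 or 0.60 requires two or three women, all of whom turn negative.

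A reader might infer something stronger: that eligibility depends on recruitment route, with a treated woman excluded if called after the visit and kept if called before it, so that the disease mix differs between routes. The documents do not establish this. Beside inclusion 5, which requires a current abnormal result, *history* can fairly be read as treatment for an earlier abnormality, and on that reading every route applies the same rule. The plan also does not state the purpose of exclusion 5, so it cannot be said that one route defeats that purpose.

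Neither argument removes the narrower point. The reading that makes the routes equal is also the one that admits post-treatment self-samples by all of them.

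**Conclusion.** The point holds in a limited form and is minor. As written, a woman treated between her clinician Pap/HPV test and a post-visit self-sample can be kept, the pair cannot be recognised from the planned data, and a negative caused by treatment would count against the kit. This is true under either reading of exclusion 5; only the set of women exposed to it differs.

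The size is about 0.06 of kappa per affected woman. It rests on the assumed table and on the assumption that she turns negative. The number of affected women is unknown and may be none.

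It should not be inferred that the change below makes the disease mix independent of recruitment route. A woman treated at the visit could still contribute a pair if she sampled beforehand, and not if she sampled after treatment. The change protects the validity of each pair and does no more than that.

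**What to change.** 1. In section 3.2, state the reference date for exclusion 5 so that all three routes apply the same rule. Which date is for the investigators to decide.
2. In section 7.1, add any cervical treatment and its date to the EMR items, taken with the colposcopy result and before the linking list in section 6.2.1.2 is destroyed.
3. In section 8.3, leave self-samples collected after such treatment out of the primary self-versus-clinician pairs, using the collection date on the requisition form. Report their number, and show the result with them included as a sensitivity analysis. A cross-reference in section 3.3.1 would make clear that this is a rule about the analysis pair.

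The cost is one EMR item and short wording changes; clinical care is unaffected. The downside is possibly a few lost pairs out of 30, and section 3.3.2 allows replacement only where time permits. If no woman is treated in the window, the change costs nothing beyond the abstraction and lets the report say so.

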3.3 Early Withdrawal of Subjects

3.3. 1 Criteria for removal from study

If the subjects becomes pregnant or does not complete the study activities they will be removed from the study.

3.3. 2 Follow-up for withdrawn subjects

The withdrawal will be documented and the subject will be replaced if the timeline allows.

4.0 Recruitment Methods

4.1 Identification of subjects

Potential participants will be identified from participating Family and Community Medicine (FCM) and OBGYN clinics at Penn State Health when they are determined to have abnormal findings on Pap/HPV test that requires a colposcopy for follow-up. Potential participants will be identified in one of three ways:

(1) A member of the study team will access the electronic medical records (EMR) for [name] and [name] OBGYN patients that meet the study criteria and have an upcoming colposcopy appointment. Then, a member of the study team will call the participant about possible involvement in the study.

(2) Clinicians will provide general information (via recruitment cards) about the study during the colposcopy appointment (if the patient was not previously contacted or was scheduled less than two weeks from their appointment). Patients will be advised to contact the study team using the information on the card if interested in participating.

(3) After a patient's appointment, if the clinician believes the individual could meet eligibility criteria for the study, the clinician will send the contact information for these patients to the study team members

through a secure message in the Electronic Medical Record. For this option, patients would not have been presented with the research opportunity during their appointment; clinicians may not have had a recruitment card available to give to their patient or may simply have forgotten to share the study opportunity.

4.2 Recruitment process

4.2. 1 How potential subjects will be recruited.

Clinicians will identify potential participants they think would be eligible for the study and provide some general information (via the recruitment cards) to the participants. Members of the study team (non-clinical staff) will prospectively review clinic schedules in order to identify potential participants, and clinicians may also identify patients after their scheduled appointment. This will ensure that enrollment numbers are met and that all potentially eligible participants are provided with a recruitment card by their clinician or contacted directly by a study team member.

4.2. 2 Where potential subjects will be recruited.

Potential subject will be recruited from Penn State Health Family & Community Medicine and OBGYN clinics.

4.2. 3 When potential subjects will be recruited.

Participants will be recruited at their colposcopy appointment in the clinician's office or over the phone by a study team member. The participant will be screened for eligibility and provide verbal implied consent.

4.2. 4 Describe the eligibility screening process and indicate whether the screening process will occur before or after obtaining informed consent. Screening begins when the investigator obtains information about or from a prospective participant in order to determine their eligibility. In some studies, these procedures may not take place unless HIPAA Authorization is obtained OR a waiver of HIPAA Authorization when applicable for the screening procedures is approved by the IRB. [For FDA regulated studies, consent for any screening activities would need to be obtained prior to screening unless specifically waived by the IRB.]

Initial screening may occur before obtaining implied consent. A member of the research team will review the EMR for FCM/ OBGYN patients that meet the study criteria. Then a study team member will call the person to complete the screening process and then obtain verbal consent. A study team member will mail the participant the study materials and a summary explanation of research.

5.0 Consent Process and Documentation

5.1 Consent Process:

Check all applicable boxes below:

Informed consent will be sought and documented with a written consent form [Complete Sections 5.2 and 5.6]

- Implied or verbal consent will be obtained – subjects will not sign a consent form (waiver of written documentation of consent) [Complete Sections 5.2, 5.3 and 5.6]**
- Informed consent will be sought but some of the elements of informed consent will be omitted or altered (e.g., deception). [Complete section 5.2, 5.4 and 5.6]**
- Informed consent will not be obtained – request to completely waive the informed consent requirement. [Complete Section 5.5]**

The following checkbox is for all locations EXCEPT Penn State Health and College of Medicine:

- Exempt Research at all Locations Except Penn State Health and the College of Medicine:** If you believe that the research activities outlined meet one or more of the criteria outlined in “HRP-312- Worksheet- Exemption Determination.” Please verify by checking this box that if conducting an exempt research study, the consent process will disclose the following (all of which are included in “HRP-590- Consent Guidance for Exempt Research”):

Penn State affiliation; name and contact information for the researcher and advisor (if the researcher is a student); the activities involve research; the procedures to be performed; participation is voluntary; that there are adequate provisions to maintain the privacy interests of subjects and the confidentiality of the data; and subjects may choose not to answer specific questions.

Note: If this box has been checked, skip the remainder of section 5 and proceed to section 6 of this protocol. If the investigator's assessment is inaccurate, an IRB Analyst will request revision to the protocol and that an informed consent form be submitted for review and approval. Except for exemptions where Limited IRB Review (see “HRP-312- Worksheet- Exemption Determination”) is required or where otherwise requested by the IRB, informed consent forms for research activities determined to be exempt without Limited IRB Review are generally not required to be submitted for review and approval by the University Park IRB.

5.2 Obtaining Informed Consent

5.2. 1 Timing and Location of Consent

Participants will be consented up to 21 days before or after their colposcopy appointment over the phone and answers will be input into REDCap by a member of the study team. Once the participant has been screened and gives verbal consent, participants will be mailed a paper copy of the summary explanation of research with the HPV self-sampling kit.

5.2. 2 Coercion or Undue Influence during Consent

After a review of the research study via the Summary Explanation of Research, subjects will be asked if they give consent to participate in the survey. Subjects will be reminded that they may refuse to answer any question and end their participation at any time, and their decision on whether or not to participate in this research will not affect their medical care.

5.3 Waiver of Written Documentation of Consent

5.3. 1 Indicate which of the following conditions applies to this research:

The research presents no more than minimal risk of harm to subjects and involves no procedures for which written consent is normally required outside of the research context.

OR

The only record linking the subject and the research would be the consent document and the principal risk would be potential harm resulting from a breach of confidentiality. Each subject will be asked whether the subject wants documentation linking the subject with the research, and the subject's wishes will govern. *(Note: This condition is not applicable for FDA-regulated research. If this category is chosen, include copies of a consent form and /or parental permission form for participants who want written documentation linking them to the research.)*

OR

If the subjects or legally authorized representatives are members of a distinct cultural group or community in which signing forms is not the norm, that the research presents no more than minimal risk of harm to subjects and provided there is an appropriate alternative mechanism for documenting that informed consent was obtained. *(Note: This condition is not applicable for FDA-regulated research.)*

Describe the alternative mechanism for documenting that informed consent was obtained:

5.3. 2 Indicate what materials, if any, will be used to inform potential subjects about the research (e.g., a letter accompanying a questionnaire, verbal script, implied consent form, or summary explanation of the research)

Verbal script (including summary explanation of the research)

5.4 Informed consent will be sought but some of the elements of informed consent will be omitted or altered (e.g., deception).

5.4. 1 Indicate the elements of informed consent to be omitted or altered

Not applicable.

5.4. 2 Indicate why the research could not practicably be carried out without the omission or alteration of consent elements

Not applicable.

5.4. 3 Describe why the research involves no more than minimal risk to subjects.

Not applicable.

5.4. 4 Describe why the alteration/omission will not adversely affect the rights and welfare of subjects.

Not applicable.

5.4. 5 If the research involves using identifiable private information or identifiable biospecimens, describe why the research could not be practicably be carried out without using such information or biospecimens in an identifiable format.

Not applicable.

5.4. 6 Debriefing

Not applicable.

5.5 Informed consent will not be obtained – request to completely waive the informed consent requirement

5.5. 1 Indicate why the research could not practicably be carried out without the waiver of consent

Not applicable.

5.5. 2 Describe why the research involves no more than minimal risk to subjects.

Not applicable.

5.5. 3 Describe why the alteration/omission will not adversely affect the rights and welfare of subjects.

Not applicable.

5.5. 4 If the research involves using identifiable private information or identifiable biospecimens, describe why the research could not be practicably be carried out without using such information or biospecimens in an identifiable format.

Not applicable.

5.5. 5 Additional pertinent information after participation

Not applicable.

